2.11.5 Derivation of resistance mechanism subgroups

[REDACTED], biomarkers are also analyzed to assign subjects in Phase Ib and Phase II to a category of the subgroups MET dysregulation status, T790M mutation status, and T790M & MET status (see [Section 2.2.2.1](#)). The resistance mechanism subgroups will be summarized by means of a frequency table (T790M & MET status) and a contingency table (MET dysregulation status vs T790M mutation status) by treatment group. Percentages will be calculated using the number of subjects in the relevant analysis set or subgroup as the denominator.

MET dysregulation status

The IHC and/or FISH results [REDACTED] will be used to determine the MET status of the subject. The subgroup categories will be assigned as follows:

- Missing, if no results are available or the available results are not sufficient (i.e. both GCN and staining category missing, MET?)
- MET dysregulated (MET+), if staining category = 3+ (defined as $\geq 50\%$ of cells staining with high intensity) or average gene copy number ≥ 4 (or both)
- MET not dysregulated (MET-), otherwise

T790M mutation status

The EGFR mutation results [REDACTED] will be used to determine the T790M status of the subject. The subgroup categories will be assigned as follows:

- T790M+, if the T790M mutation is reported [REDACTED]
- T790M-, if it is reported that a T790M mutation was not found [REDACTED]
- T790M?, if the test result is reported as Unknown, Not evaluable, or Not analyzed/analyzable or is completely missing

Please also see [Section 4](#).

T790M & MET status

The subgroups of combined and marginal T790M and MET status will be determined from the above MET dysregulation and T790M mutation status:

T790M+ & MET+	T790M+ & MET-	T790M+ & MET?
T790M- & MET+	T790M- & MET-	T790M- & MET?
T790M? & MET+	T790M? & MET-	T790M? & MET?
T790M+	T790M-	T790M?
MET+	MET-	MET?

Only categories present in the data will be presented and not all categories might be presented in all outputs (e.g. in-text outputs).

MET amplification status

Categories for MET amplification status, i.e. GCN alone, are:

- <4
- 4-6
- ≥ 6
- failed or missing

The failed or missing category might not be presented in all outputs.

MET expression status

Categories for MET expression status, i.e. IHC staining category alone, are:

- 0+
- 1+
- 2+
- 3+
- failed or missing

The failed or missing category might not be presented in all outputs.

2.11.6 Biomarker analysis

Unless otherwise specified, the analyses will be presented separately for Phase Ib and Phase II subjects.

2.12 Other exploratory analyses

Not applicable.

2.13 Interim analysis

2.13.1 Phase Ib part

No formal interim analyses are planned. However, the dose-escalation design foresees that decisions based on the current data are taken before the end of the study. More precisely, after each cohort in the dose-escalation part, the next dose will be chosen depending on the observed data. Details of this procedure and the process for communication with investigators are provided in [\[CSP Section 6.2.3\]](#).

2.13.2 Phase II part

The futility interim analysis was conducted for subjects enrolled in Group 3 (EGFRmut, T790M negative, any MET, 1L antineoplastic) with 21 subjects who had completed at least 4 cycles of treatment or discontinued treatment prior to that time (see [primary CSR] for details and results).

3 Sample size calculation

Please refer to the [Primary CSR] for details about sample size calculations.

4 Change to protocol specified analyses

Hepatotoxicity

To implement the Novartis Hepatotoxicity Guideline released in 2019, the analysis of liver function parameters was modified accordingly.

COVID-19

Analysis of protocol deviations related to COVID-19 were added.

Imputation rules

Imputation rules for partial dates of anti-cancer therapies were updated.

5 Appendix

5.1 Imputation rules

5.1.1 Investigational drug

The following rule should be used for the imputation of the dose end date for a given study treatment component:

Scenario 1: If the dose end date is completely missing and there is no EOT page and no death date, the subject is considered as on-going

The subject should be treated as on-going and the cut-off date should be used as the dose end date. Scenario 1 should not be applicable for the final CSR. All subjects in the current analysis have the EOT page completed before DBL for the final CSR.

Scenario 2: If the dose end date is completely or partially missing and the EOT page is available

- Case 1: The dose end date is completely missing and the EOT completion date is complete, then this latter date should be used
- Case 2: Only year (YYYY) of the dose end date is available and YYYY < the year of EOT date, then use 31DECYYYY

- Case 3: Only year (YYYY) of the dose end date is available and YYYY = the year of EOT date, then use EOT date
- Case 4: Both year (YYYY) and month (MMM) are available for dose end date and YYYY = the year of EOT date and MMM < the month of EOT date, then use last day of the Month (MMM)

All other cases should be considered as a data issue and the statistician should contact the data manager of the study.

After imputation, compare the imputed date with start date of treatment

- If the imputed date is < start date of treatment, then use the treatment start date
- Otherwise, use the imputed date

Subjects with missing start dates are to be considered missing for all study treatment component related calculations and no imputation will be made. If start date is missing then end-date should not be imputed.

5.1.2 AE date imputation

Table 5-1 Imputation of start dates (AE, CM) and assessments (LB, EG, VS)

Missing element	Rule
Day, month, and year	No imputation will be done for completely missing dates
Day, month	
 • If available year = year of study treatment start date then 
 • If stop date contains a full date and stop date is earlier than study treatment start date then set start date = 01JanYYYY • Else set start date = study treatment start date • If available year > year of study treatment start date then 01JanYYYY • If available year < year of study treatment start date then 01JulYYYY
Day	
 • If available month and year = month and year of study treatment start date then 
 • If stop date contains a full date and stop date is earlier than study treatment start date then set start date= 01MonYYYY • Else set start date = study treatment start date • If available month and year > month and year of study treatment start date then 01MonYYYY • If available month and year < month year of study treatment start date then 15MonYYYY

Table 5-2 Imputation of end dates (AE, CM)

Missing element	Rule
Day, month, and year	• Completely missing end dates (incl. ongoing events) will be imputed by the end date of the on-treatment period *
Day, month	• If partial end date contains year only, set end date = earliest of 31DecYYYY and end date of the on-treatment period *
Day	• If partial end date contains month and year, set end date = earliest of last day of the month and end date of the on-treatment period *

Missing element	Rule
-----------------	------

* last treatment date plus 30 days not > (death date, cut-off date, withdrawal of consent date)

Any AEs and concomitant medications with partial/missing dates will be displayed as such in the data listings.

Any AEs and concomitant medications which are continuing as per data cut-off will be shown as 'ongoing' rather than the end date provided.

The above imputations are only used for analyses of time to and duration of AEs and concomitant medications.

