[figure not shown]
The protocol allows radiotherapy to the bone or central nervous system (CNS), and surgical resection of CNS metastases as well as palliative bone radiotherapy (that is, these will not lead to censoring).

Derivation of new anti-cancer therapy

To determine the use of new anti-cancer therapy, data entered in the following CRFs will be considered [REDACTED]:

- Antineoplastic Therapy Since Discontinuation of Study Treatment – Medication,
- Antineoplastic Therapy Since Discontinuation of Study Treatment – Radiotherapy,
- Antineoplastic Therapy Since Discontinuation of Study Treatment – Surgery.

In addition certain therapies entered in the CRF Prior and Concomitant Medications (domain CM) will be considered, if they were started after start of study treatment.

2.5.2.5 Primary endpoint – Phase II Group 4

Frequencies of treatment-emergent AEs will be calculated to characterize the safety and tolerability of the study treatment. The Safety Set will be used for summary tables.

2.5.2.6 Statistical hypothesis, model, and method of analysis – Phase II Group 4

Adverse events will be analyzed as described in the section on safety analysis, [Section 2.8.1](#).

2.5.2.7 Handling of missing values/censoring/discontinuations – Phase II Group 4

Summary tables for AEs will include events collected in the on-treatment period. If dates are incomplete and no clear assignment to pre-, on-, or post-treatment period can be made, then on-treatment will be assumed (see [Section 5.1.2](#)).

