Day, month, and year	For completely missing start dates, set to study treatment end date + 1

If the end date is not missing and the imputed start date is after the end date, use the end date as the imputed start date.

In case there are any scenarios found in the final data that are not covered by the rules above, they will be handled in the respective dataset program and documented in the PDS.

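### The AE and medication date rules in SAP section 5.1.2 can impute dates that the record rules out, and their stated scope conflicts with section 2.5.2.7

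*SAP*

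**What the plan says.** **Start dates (SAP 5.1.2, Table 5-1).** For a start with only the year known, in the year of first dose: "If stop date contains a full date and stop date is earlier than study treatment start date then set start date = 01JanYYYY". In all other cases in that year: "Else set start date = study treatment start date". The row for a missing day uses the same two branches within the month of first dose. A year-only start in an earlier year goes to 1 July of that year, and a day-missing start in an earlier month goes to the 15th.

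**End dates (Table 5-2).** With the day missing: "set end date = earliest of last day of the month and end date of the on-treatment period". With only the year known: "set end date = earliest of 31DecYYYY and end date of the on-treatment period". Completely missing end dates, including ongoing events, take the end of the on-treatment period. That date is the last treatment date plus 30 days, limited by death, cut-off and consent withdrawal. Full end dates have no cap.

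**Scope.** Section 5.1.2 closes with: "The above imputations are only used for analyses of time to and duration of AEs and concomitant medications". Section 2.5.2.7, which covers the AE tables that are Group 4's primary endpoint, says that if dates are incomplete and "no clear assignment to pre-, on-, or post-treatment period can be made, then on-treatment will be assumed", and it refers to 5.1.2. Section 2.1.4 has the same default and defines treatment-emergent AEs by a start date in the on-treatment period.

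**Order check.** For prior antineoplastic therapies, section 5.1.3 has a rule beginning "If the end date is not missing and the imputed start date is after the end date", which resets the start to the end date. A second sentence does the same when both dates are imputed. For post-treatment therapies only the first rule is given. Section 5.1.2 has neither.

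**The concern.** A partial date still carries information. A stop recorded as February 2016 shows that an event was over before a first dose on 10 March 2016, even without the day. Table 5-1 ignores this unless the day is present, and Table 5-2 overrides a recorded end month that falls after the on-treatment period. With no order check, the two tables together can end an event before it starts.

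The first thing at stake is any time-to or duration output for AEs and concomitant medications, and study day in listings, which section 2.1.4 allows to be calculated from imputed dates. The second is indirect. Because section 2.5.2.7 points to 5.1.2, a programmer could run AE starts through Table 5-1 before deciding treatment-emergent status.

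**Working it through.** The plan gives no figure to reproduce, so the check applies both tables literally to test records. The SAP supplies no such dates, and those below are assumptions. Duration is taken as end − start + 1, the form used for exposure in section 2.4.1.

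**Set A.** First dose 10Mar2016. Start recorded as 2016, stop as Feb 2016.
- Table 5-1: the year equals the first-dose year and the stop date is not full, so start = 10Mar2016.
- Table 5-2: the last day of the month is earlier than the period end, so end = 29Feb2016.
- Duration = 29Feb2016 − 10Mar2016 + 1 = −10 + 1 = −9 days.

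**Set B.** First dose 15Jun2017, last dose 10May2018. On-treatment period ends 10May2018 + 30 = 09Jun2018.

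| Recorded start | Recorded end | Imputed or used | Duration (days) |
|---|---|---|---|
| 2017 | 20Mar2017 | 01Jan2017 to 20Mar2017 | 79 |
| 2017 | Mar 2017 | 15Jun2017 to 31Mar2017 | −75 |
| 01May2018 | 15Aug2018 | unchanged | 107 |
| 01May2018 | Aug 2018 | 01May2018 to 09Jun2018 | 40 |
| 01Jul2018 | Aug 2018 | 01Jul2018 to 09Jun2018 | −21 |
| 2016 | 10Mar2016 | 01Jul2016 to 10Mar2016 | −112 |
| Apr 2017 | 05Apr2017 | 15Apr2017 to 05Apr2017 | −9 |

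- Rows 1 and 2 differ only in whether the stop day was recorded. One is a valid pre-dose event and the other is reversed.
- Rows 3 and 4 also differ only in the day. For row 4 the record allows 93 days (end 01Aug2018) to 123 days (end 31Aug2018). The imputed 40 days lies outside that range.
- Row 5 is an event that began after the on-treatment period. The cap puts its end before its start.
- Rows 6 and 7 have full stop dates and still reverse, because Table 5-1 assigns mid-year or mid-month starts for earlier periods without looking at the stop date. The missing order check is therefore a gap of its own.

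**Where the partial-stop fault can occur.** It arises only in the year-only row. In the day-missing row the start month is the first-dose month, so a valid partial stop cannot have its last possible day before first dose.

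**Scope, side by side.** The closing sentence of 5.1.2 rules out using these imputations for period assignment. Section 2.5.2.7 refers to 5.1.2 on exactly that matter. The title of Table 5-1 also covers laboratory, ECG and vital-sign assessments, and section 2.1.4 allows study day from imputed dates. The closing sentence covers none of these uses.

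**Size if 5.1.2 did drive the AE tables.** Group 4 has about 30 subjects, so each subject wrongly counted would add 1/30 = 3.3 percentage points to a preferred-term rate.

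**The case against.** The strongest reply concerns the consequence. A reader might infer that pre-dose events become treatment-emergent under this plan. The documents do not say so. Section 5.1.2 confines its imputations to time-to and duration analyses, and sections 2.1.4 and 2.5.2.7 fall back on on-treatment only when no clear assignment is possible. An event whose recorded stop month precedes first dose can be assigned clearly to the pre-treatment period. Likewise, section 2.4.2 decides concomitant use from start and continuation relative to first dose, so a recorded stop month before first dose settles that too. This stands. What remains is a cross-reference that contradicts the scope sentence.

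A second reply is that the Table 5-2 cap is a convention: safety summaries cover the on-treatment period, so durations end there. That is reasonable, and completely missing and ongoing end dates are treated the same way. But the convention is not applied to full end dates, and it yields a negative duration for an event that began after the period.

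Third, the visible SAP lists no duration or time-to table for AEs or medications; section 2.8.1 gives incidence tables and section 2.4.2 gives frequencies. Some text is redacted, so this cannot be taken as final, but it limits the likely effect. The record patterns are also uncommon: the partial-stop fault needs a year-only start in the first-dose year together with a day-missing stop in an earlier month.

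**Conclusion.** The concern holds as a fault in the stated date rules. Read literally, Tables 5-1 and 5-2 produce impossible dates (−9 days in Set A; −75, −21, −112 and −9 in Set B) and make duration depend on whether a day was recorded (40 against 107 days). The order check that would stop most of the reversals exists in section 5.1.3 but not here. The scope sentence of 5.1.2 and the reference in section 2.5.2.7 conflict and must be reconciled.

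False treatment-emergent events in Group 4's primary endpoint are a risk only if section 2.5.2.7 is followed through Table 5-1; they are not a stated result. The example dates are assumed, and the number of partial AE and medication dates is not given. It is probably small, so this is a minor correction.

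**What to change.** 1. **Table 5-1, year-only row:** apply the exception when the latest possible stop date (the full date, or the last day of the recorded month) is before first dose. The Set A event then runs from 01Jan2016 to 29Feb2016 (31 + 29 = 60 days) and is pre-treatment. The day-missing row needs no change.
2. **Order checks:** add to 5.1.2 both checks that section 5.1.3 gives for prior antineoplastic therapies. The check for two imputed dates is the one that covers Set A; the check for a recorded end date covers rows 6 and 7.
3. **Table 5-2:** state whether duration means on-treatment duration. Apply one cap to full, partial and ongoing end dates, and never impute an end before the start. Lifting the cap for partial dates alone would not do, because an event with a recorded later end month could then last longer than one still ongoing. Settle this before adding the order checks. Otherwise a start of Jul 2018 with an end of Aug 2018 in Set B would have its start pulled back from 01Jul2018 to the capped end, 09Jun2018, which is inside the on-treatment period.
4. **Scope:** make the last sentence of 5.1.2 agree with section 2.5.2.7, and state that an event whose recorded stop month precedes first dose is pre-treatment.

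The cost is a few lines of SAP text and a small change to the date-imputation program. No new data are needed.

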5.1.3 Other imputations

Incomplete date of initial diagnosis of cancer and date of most recent recurrence

Missing day is defaulted to the 15th of the month and missing month and day is defaulted to 01Jan.

If because of this imputation the chronology of the events is altered then the imputation should be made to the minimum value up to where chronology remains unchanged. E.g. if due to imputation the date of most recent recurrence becomes prior to the initial diagnosis date then it should be set to initial diagnosis date.

Incomplete assessment dates for tumor assessment

All investigation dates (e.g. MRI scan, CT scan) must be completed with day, month and year. If one or more assessment dates are incomplete but other investigation dates are available, this/these incomplete date(s) are not considered for calculation of the assessment date and assessment date is calculated as the latest of all investigation dates (e.g. MRI scan, CT scan) if the overall response at that assessment is CR/PR/SD/UNK. Otherwise – if overall response is progression – the assessment date is calculated as the earliest date of all investigation dates at that evaluation number. If all measurement dates have no day recorded, the 1st of the month is used. If the month is not completed, for any of the investigations, the respective assessment will be considered to be at the date which is exactly between the previous and following assessment. If a previous and following assessment is not available, this assessment will not be used for any calculation.

Applying the cut-off to tumor assessment

For tumor related assessments, if an evaluation has some assessments done prior to cut-off date and others after the cut-off date, then the evaluation is considered post-cut-off date and will be excluded from analysis.

Incomplete or missing death date

For cases when either day is missing or both month and day are missing for the date of death, the following imputation rules will be implemented:

- If only day is missing, then impute the 15th day of the month and year of death

- If both day and month are missing, then impute 01Jul of the year of death

Prior antineoplastic therapies date imputation

- Start dates
The same rule which is applied to the imputation of AE/concomitant medication start dates will be used with the following exception:
 - If month and day are missing and the available year = year of study treatment start date, then impute with study treatment start date – 1
- End dates
 - If day is missing, imputed date = min(reference end date, last day of the month)
 - If month and day are missing, imputed date = min(reference end date, 31Dec)

Reference end date will be the start date of study treatment.

If the end date is not missing and the imputed start date is after the end date, use the end date as the imputed start date. If both the start date and the end date are imputed and if the imputed start date is after the imputed end date, use the imputed end date as the imputation for the start date.

Post-treatment antineoplastic therapies date imputation

For new antineoplastic (ANP) therapies starting after study treatment was discontinued or starting while study treatment was still ongoing (protocol deviation), a missing or partial start date of this new therapy will be imputed as specified in [Table 5-3](#).

The complete (imputed) dates are required for censoring of efficacy endpoints. Therefore, partial or missing start dates will only be imputed for the first such therapy. Partial or missing end dates of the first new therapy and any partial or missing dates of second or later new antineoplastic therapies will not be imputed.

Table 5-3 Imputation of start dates for post-treatment antineoplastic medications

Missing element	Rule
Day	
 • If available year \geq year of study treatment end date then ANP start date = max(study treatment end date + 1, 01MonYYYY) • If available year < year of study treatment end date then ANP start date = max(study treatment start date + 1, 01MonYYYY)
Day, month	
 • If available year = year of study treatment end date then ANP start date = min(study treatment end date + 1, 31DecYYYY) • If available year > year of study treatment end date then ANP start date = 01JanYYYY • If available year < year of study treatment end date, 
 • If available year < year of study treatment start date, do not impute • If available year > year of study treatment start date, then ANP start date = 01JulYYYY • If available year = year of study treatment start date and day/month of study treatment start date < 01JulYYYY, then ANP start date = 01JulYYYY

Missing element	Rule
	
 If available year = year of study treatment end date and day/month of study treatment start date \geq 01JulYYYY, then ANP start date = min(middle between the treatment start and end date, 31DecYYYY)
Day, month, and year	For completely missing start dates, set to study treatment end date + 1

If the end date is not missing and the imputed start date is after the end date, use the end date as the imputed start date.

In case there are any scenarios found in the final data that are not covered by the rules above, they will be handled in the respective dataset program and documented in the PDS.

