PFS is defined as the time from the date of first administration of study treatment to the date of the first documented progression or death due to any cause. PFS will be based on local investigators or BIRC review of tumor assessments and using RECIST 1.1 criteria (see [CSP Appendix 1]). PFS will be censored at the date of the last adequate tumor assessment if no PFS event is observed prior to the analysis cut-off date [REDACTED] or before the start of the new anti-cancer therapy date, whichever is earlier. (See Section 2.7.3 for additional details regarding censoring rules and determination of date of last adequate tumor assessment, see Section 2.5.2.1 regarding exceptions in determining anti-cancer therapy usage). Discontinuation due to disease progression (collected on the ‘End of treatment’ and ‘End of post treatment follow up’ disposition pages without supporting objective evidence satisfying progression criteria per RECIST 1.1 will not be considered disease progression for PFS derivation. Clinical deterioration will not be considered as a qualifying event for progression.

Overall survival

OS is defined as the time from date of first administration of study treatment to date of death due to any cause. All deaths occurring on or before the efficacy cut-off date will be used in the OS analysis. If a subject is not known to have died at the time of the analysis, the OS time will be censored at the date of last contact.

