2.7.3 Handling of missing values/censoring/discontinuations

ORR

See [Section 2.5.2.3](#).

TTR

Subjects who did not achieve a confirmed PR or CR will be censored as described in [Section 2.7.1](#).

DOR

Subjects continuing without progression or death will be censored at the date of their last adequate tumor assessment using the censoring rule described for the PFS analysis.

PFS

PFS will be censored at the date of the last adequate tumor assessment if no PFS event is observed prior to the [REDACTED] analysis cut-off date or before the start of the new anti-cancer therapy date, whichever is earlier.

The date of last adequate tumor assessment is the date of the last tumor assessment with overall lesion response of CR, PR or SD before an event or a censoring reason occurred. In this case the last tumor evaluation date at that assessment will be used. If no post-baseline assessments are available (before an event or a censoring reason occurred) then the start date of treatment will be used.

In particular, PFS will be censored at the last adequate tumor assessment if one of the following occurs: absence of event; the event occurred after a new anti-cancer therapy was administered (see also [Section 2.5.2.3](#)); the event occurred after two or more missing tumor assessments.

The term ‘missing adequate tumor assessment’ is defined as a TA not performed or TA with overall lesion response of ‘UNK’. The rule to determine the number of missing TAs is based on the time interval between the date of last adequate tumor assessment and the date of an event. If the interval is greater than twice the protocol-specified interval between the TAs and 2 times the protocol-allowed time window around assessments, then the number of missing assessments will be 2 or more.

Refer to [Table 2-4](#) for censoring and event date options and outcomes for PFS.

Table 2-4 Outcome and event/censor dates for PFS analysis

Situation	Date	Outcome
No baseline assessment	Start date of treatment	Censored
Progression or death at or before next scheduled assessment	Date of progression (or death)	Progressed
Progression or death after exactly one missing assessment	Date of progression (or death)	Progressed
Progression or death after two or more missing assessments	Date of last adequate assessment prior to missed assessment	Censored
No progression (or death)	Date of last adequate assessment	Censored

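### The missing-month rule for tumour scans is ambiguous, and it leaves a progression at the last evaluation undated and, as written, unused

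*SAP*

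**What the plan says.** The paragraph on incomplete tumour assessment dates in SAP section 5.1.3 opens with a requirement: "All investigation dates (e.g. MRI scan, CT scan) must be completed with day, month and year". It then gives rules for dates that are incomplete all the same.

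- **Some dates incomplete, others available:** "this/these incomplete date(s) are not considered for calculation of the assessment date". The evaluation is dated from the remaining scans. For a progression, "the assessment date is calculated as the earliest date of all investigation dates at that evaluation number".
- **Day missing:** "If all measurement dates have no day recorded, the 1st of the month is used".
- **Month missing:** "If the month is not completed, for any of the investigations, the respective assessment will be considered to be at the date". The date meant is the one halfway from the previous assessment to the following one.
- **Neighbours lacking:** "If a previous and following assessment is not available, this assessment will not be used for any calculation".

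No order of precedence is stated, and progression is not exempted from the last rule.

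Section 2.7.1 gives this definition of PFS: "the time from the date of first administration of study treatment to the date of the first documented progression or death due to any cause". Section 2.7.3 sets the censoring: "PFS will be censored at the date of the last adequate tumor assessment if no PFS event is observed prior to the". That sentence goes on to name two limits, the cut-off for the analysis and the start of new anti-cancer therapy. DOR follows the same censoring rule.

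**The concern.** A midpoint needs an assessment on each side. Progression is often the last evaluation a subject has, so the missing-month rule can fail on a record that carries the event. If the evaluation is then set aside, a progression that was seen and recorded is lost because of a date field, which conflicts with the PFS definition. The resulting censoring is informative, because the subject is censored just before a known progression.

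The SAP is more forgiving elsewhere in the same section. A death lacking day and month is kept and set to 1 July. A first new anti-cancer therapy with no start date at all is kept and set to the day after treatment ended. An undatable final progression gets no such treatment.

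The second problem is the trigger. The missing-day rule speaks of all dates, while the missing-month rule speaks of any investigation. Two programmers could treat an evaluation with one full date and one month-less date differently.

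**Working it through.** The SAP states no figure on this point, so the check applies its rules to constructed records.

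**Step 1: which rule governs.**

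| Record | Month rule means at least one scan lacks a month | Month rule means no scan has a month |
|---|---|---|
| One full date, one without month; following scan exists | Midpoint | Date of the full scan |
| One full date, one without month; no following scan | No midpoint; evaluation dropped | Date of the full scan |
| No scan has a month; no following scan | No midpoint; evaluation dropped | No midpoint; evaluation dropped |

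The third row is the same under both readings. If the final sentence is taken to apply only when both neighbours are absent, a last evaluation with a previous assessment has no rule at all. It still has no date.

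In the first row the choice matters little. With even spacing the midpoint equals the scan date. If the following scan is 3 weeks early or late, the midpoint moves by 21/2 = 10.5 days.

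**Step 2: effect on PFS when a final progression is dropped.** The SAP gives neither the scan interval nor the visit window, so these are assumed: interval I = 6, 8 or 12 weeks, window w = 1 or 2 weeks. The last SD scan is 2 intervals after first dose and the progression scan 3 intervals after. Counting first dose as day 1, with the SAP's month of 30.4375 days, time = (7 × k × I + 1) / 30.4375 for k intervals.

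| I (weeks) | Progression kept: event | Progression dropped: censored |
|---|---|---|
| 6 | (126 + 1)/30.4375 = 4.17 months | (84 + 1)/30.4375 = 2.79 months |
| 8 | (168 + 1)/30.4375 = 5.55 months | (112 + 1)/30.4375 = 3.71 months |
| 12 | (252 + 1)/30.4375 = 8.31 months | (168 + 1)/30.4375 = 5.55 months |

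The middle column is the result when a fully dated scan is used, or when the true date is known.

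**Step 3: whether a later death restores the event.** Section 2.7.3 censors an event that falls more than 2 intervals plus 2 windows after the last adequate assessment. Measured from the dropped scan, death still counts up to 14I + 14w − 7I = 7I + 14w days, provided no new anti-cancer therapy came first.

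| I (weeks) | w = 1 | w = 2 | Death 30 days after the dropped scan |
|---|---|---|---|
| 6 | 42 + 14 = 56 days | 42 + 28 = 70 days | event at 157/30.4375 = 5.16 months |
| 8 | 56 + 14 = 70 days | 56 + 28 = 84 days | event at 199/30.4375 = 6.54 months |
| 12 | 84 + 14 = 98 days | 84 + 28 = 112 days | event at 283/30.4375 = 9.30 months |

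A death 180 days after the dropped scan lies beyond every limit, so the subject is censored at the previous scan. Where death does count, the event is dated later than the progression.

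**Step 4: best overall response.** Under section 2.5.2.1 a subject with no qualifying CR, PR or SD is PD if progression came within 17 weeks, and otherwise UNK. Dropping the only evaluation that shows progression can therefore turn PD into UNK. Section 2.5.2.3 makes an exception where progression is reported, but section 5.1.3 bars the evaluation from every calculation, so the result is not settled. ORR is unaffected by this change, since both categories count as failures.

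**The case against.** The strongest defence reads the paragraph as a cascade: ignore incomplete dates if another is available; use the 1st if every date lacks its day; use the midpoint if no scan has a month. On that reading a fully dated scan settles a mixed evaluation and nothing conflicts. The reading is tenable. A reader might infer that the SAP plainly contradicts itself, but the text supports only an unresolved ambiguity.

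Three other strong inferences also fail.

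- *The rule strikes almost only progressions and biases one way.* It equally drops a final SD, CR or PR scan. That moves a censoring date earlier or, if the scan was the confirming one, can cost the subject a confirmed response and lower ORR.
- *Every dropped progression becomes a censoring.* Step 3 shows that a timely death remains an event.
- *About 2.5% of a group is affected.* One record in a group of 40 is 1/40 = 2.5%, but that is the weight of one record and says nothing about how many there are.

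It is also fair to say that full dates are required, that PFS and DOR are secondary descriptive summaries, and that the Phase II primary objective has already been reported in the primary CSR. Section 5.1.3 ends by leaving uncovered scenarios to the dataset program. That sentence follows the rules for post-treatment therapy, and even if read widely it would leave the choice between event and censoring until the data are in hand.

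These points limit how often the problem arises and how much it weighs. They supply no date for a final progression in which no scan has a month.

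**Conclusion.** The point holds in a limited form. The missing-month rule is ambiguous for an evaluation that also has a fully dated scan. Under either reading, a last evaluation in which no scan has a month receives no date and, read with the final sentence, is dropped even if it shows progression. The consequence is a PFS or DOR censoring at the previous adequate scan, or a later-dated death event, and possibly a best overall response of UNK in place of PD.

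For one affected subject without a timely death, an event at 4.17, 5.55 or 8.31 months becomes a censoring at 2.79, 3.71 or 5.55 months. These figures rest on the assumed 6-, 8- and 12-week intervals. The number of such records is probably very small, and the SAP gives no count. The rule deserves correction because, as stated, it can erase an observed event and the correction is nearly free. It is not evidence that the reported PFS or DOR is materially biased.

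**What to change.** Make two changes to section 5.1.3.

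1. State that the missing-month rule applies only when no investigation in the evaluation has a usable date, meaning at least month and year. Change the trigger from any investigation to all investigations. A mixed evaluation is then dated from its usable scans.
2. State that a progression evaluation without a following assessment is kept as an event. Pre-specify its date, bounded below by the previous assessment and above by the recorded year or visit and by death or cut-off. State that the imputed date must not itself trigger the censoring for two or more missing assessments.

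An open-ended midpoint to last contact or cut-off would not serve: it could fall far from the scan and set off that same censoring.

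The cost is two sentences of SAP text, a small change to the derivation program, and an approximate event date for any such record.
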